Prior to being filled, empty capsules and lactose excipient are stored in an airtight bag in a gasket sealed plastic box, in a cabinet in a lab that does not utilize scintillation detectable radioactivity or human tissues.

Each capsule contains only the [¹⁴C]-BaP test article product and lactose as an excipient. Solaray Size 0 empty vegetarian capsules, composed of vegetable cellulose, will be opened and held in a microtube rack. The empty capsules will be filled with pharmaceutical grade lactose monohydrate (Spectrum Chemical Mfg Group). The 25 μ L aliquot of dosing solution of the chosen concentration (25, 50, 100 or 250 ng [¹⁴C]-BaP) will be applied to the lactose in each of the 5 capsules using a calibrated pipet fitted with a sterile filter tip. The ethanol will be allowed to evaporate, then the capsules will be sealed with capsule caps.

Immediately after capsule preparation, 3 of the 5 capsules will be dissolved in 5 ml water and 20 ml scintillant and counted on a liquid scintillation counter. Results will be emailed directly to [name], the director of OSU Radiation Safety (RSO). Once RSO has determined that the three evaluated capsules are within 10% variance and 10% error, the results are emailed to [name]. [name] will then contact [name] and [name] that the cycle may proceed. If the capsules are not given RSO approval, the participant is rescheduled and a new set of capsule will be prepared. Two capsules will be stored in sealed vials in the dark in a zipper-lock plastic bag with silica desiccant at -20°C until subject consumption. One capsule per cycle will be given to subjects. The remaining capsule will be for back-up in case of any problems or disposed in radioactive dry waste if not needed. Any capsules not used within 1 week will be discarded.

Dispensing: Capsules will be transported to the Clinical Research Center (407 LPSC) in sealed glass vials within a zipper-lock polypropylene bag for secondary containment. The bag will be labeled as described above and stored within a plastic box for transportation to the clinic.

One capsule containing 25, 50, 100 or 250 ng [¹⁴C]-BaP will be administered to subjects with 100 mL of water by the nurse coordinator at the start of the study cycle.

Inventory control: Information including number of capsules, date of preparation, and operator are recorded immediately after capsules are prepared. Date of consumption and disposal of test capsules are recorded on day 1 of the cycle. If test capsules do not pass approval by the OSU radiation safety officer, the information is still recorded and a new set of capsules will be prepared.

Disposal: Capsules that are not needed, expired or rejected for human use will be disposed of in the radiochemical waste at Oregon State University.

- Explain whether the use of the test article involve a route of administration or dosage level, use in a subject population, or other factor that significantly increases the risks (or decreases the acceptability of the risks) associated with its use:

The great majority of exposure (>95%) of the larger molecular weight PAHs, such as BaP, is through the diet in a variety of foods including breads and cereals, grains, vegetables and smoke-cured or barbequed meats². Dietary intakes of total PAHs in the U.S. have been estimated at 160-1600 ng/day with BaP alone at 270-700 ng/day. A 2005 report from the FAO/WHO Joint Expert Committee on Food Additives and Contaminants listed a mean BaP daily dietary intake of 270 ng (70 Kg individual) with 700 ng as a high-level intake¹. The European Union maximum limit for BaP in smoked meats is 5,000 ng/Kg fresh weight. The dose of 250 ng would be the equivalent of approximately 45 g of smoked meat at the EU allowable limit. Compiling all of the animal data, a **Virtually Safe (Lifetime) Dose (VSD) of 42-350 ng/person/day** has been established as the best estimate for a lifetime exposure to BaP producing no more than 1 cancer per million people¹⁻⁴. Therefore, based on the chemical mass involved in microdosing (significantly lower than

background exposure and levels determined to be VSD), this study poses *de minimus* risk to subjects.

22. Food. Subjects will be provided breakfast on the first morning of each cycle. Up to \$10 worth of food and/or beverage will be purchased at Ava's Café in LPSC or another local café.

23. Medical Devices- N/A.

24. Radiation- Radiation Safety approval form included.

It should be noted that in our study, a cumulative total of 45.9 nCi for the 4 dose cycles of [¹⁴C]-BaP is equivalent to about 170 minutes of natural background radiation. Patients have been given 1,000 nCi of ¹⁴C in the urea breath test for the diagnosis of *Helicobacter pylori*¹³ and a recent study utilized a dose to human volunteers of 300,000 nCi of [¹⁴C]-epicatechin (a polyphenol from green tea)¹⁴. The chemical form of ¹⁴C (BaP) to be used in the present study can not be broken down to CO₂, as in the urea breath test, and thus could not be incorporated into metabolic pathways in the body. In animal studies, PAHs are eliminated rapidly (hours to days) from the body and this has been confirmed by our PAH microdosing study with dibenzo[def,p]chrysene (Figure 1).^{7,8}

[figure not shown]

Figure 1. Pharmacokinetics of DBC in Humans Following a Dose of 5 nCi (29 ng) (IRB Protocol #3853)

25. Biological Samples

- A Biological Materials Form is included.
- Biological samples as described above in the Methods and Procedures section will be obtained from living subjects, prospectively, for this research.
- The total amount of blood collected from each subject is 480 mL (4 x 120 mL/cycle). The maximum amount of blood collected in an 8 week period is 240 mL.
- Samples will be identified by a code that will be protected as described in the Anonymity and Confidentiality section below. A portion of the de-identified coded study samples will be forwarded to LLNL for analysis with no personal identifying information contained within the shipment, so there is no risk of loss of confidentiality with the mailing of samples to LLNL nor the analysis of samples at LLNL. The remaining coded samples will be stored in LPSC 389 at OSU

indefinitely unless not allowed by subjects (see Anonymity and Confidentiality section). Coded samples will be retained for potential future research projects relating to the study objectives. The consent form includes a section for subjects to give permission to use their samples in future projects without being contacted for consent.

- Samples sent to LLNL will be processed at OSU before shipment and are no longer considered biohazardous materials after processing. The radioactivity level in collected blood and urine are well below what is considered a background level when we conduct routine laboratory swipe surveys (below the limit of detection by liquid scintillation counting) and thus, these samples are not considered radioactive material. OSU personnel processing the samples are not exposed to above background levels of radioisotopes and /or carcinogen. This material does not pose a biohazard, carcinogen hazard, or radioactivity health risk to postal carriers or LLNL employees.
- No medical records will be accessed.
- Only urine pregnancy tests will be conducted with female subjects at the screening visit and before each cycle. No results will be shared with subjects.
- Although one of the study aims is to determine if there is genetic variability between subjects that could account for variability in study outcomes, this is not “genetic testing” in the usual sense as only a few genes will be assessed for allelic variants and results will not be disclosed to subjects (as there is no established relationship between any of the allelic variants and disease). Coded samples will be stored in LPSC 389 at OSU indefinitely unless not allowed by subjects (see Anonymity or Confidentiality section). Coded samples will be retained for potential future research projects relating to the study objectives.
- DNA will be stored and not shared. Subjects will not be contacted in the future as there will be no relevant clinical data to share. The subject can indicate on the consent form whether or not he/she agree to have a small number of genes (maximum 7) known to be involved in metabolism and excretion of BaP analyzed. The results will not be shared as there is no established disease risk; no family relationships will be tested or disclosed. For disclosure of clinically relevant information see bullet above.
- Plasma extracts and urine samples will not be returned from Lawrence Livermore National Laboratories but will be discarded by them upon completion of their analysis.

26. Anonymity or Confidentiality

- We will handle all research records as confidentially as possible and retain for three years post-study termination. We will protect all computer records by passwords and keep all paper study records in a locked cabinet in a locked room accessible only to the study team.
- Only the nurse coordinator will have access to the document linking identifiers to subject code numbers. Personal information collected during telephone screening, the consent documents, and compensation acknowledgement form will be the only documents containing subject name and personal information. We will collect direct identifiers (name, mailing address, email and phone number) for the purpose of contacting the subject throughout the course of the study. We will store this information separately from coded data. Health assessment, subject demographic documents and other research information obtained during the duration of the study will also be identified only by ID code and kept in a location separate from any materials that may identify the subjects.

- At the completion of the data analysis of the study, we will keep only coded sample data. At this time, we will shred and destroy any information linking individual identifiers to subject codes.
- We will not provide materials containing ID codes and personal identifiers to anyone outside the research team. Also, we will not use individual identities in reports or publications resulting from this study. This study does not involve medical, educational or other personal records.
- We will report names of subjects enrolled from the CHAR Life Registry back to CHAR at the completion of the recruitment phase or earlier if requested.
- Data will be reported in publications in aggregate or coded such that subjects will not be identifiable.
- Any information stored electronically will be on a computer system with a fully patched operating system and applications, and current antivirus software with current virus definitions and a plan for routine back-ups is in place.
- We will protect email correspondence by deleting after the subject has completed the study, is removed or withdraws from the study, or has been found to not qualify.
- We will only identify biological samples collected during the study by non-identifying code. We will process in-house or to LLNL for analyses with no personal information of the subjects provided.
- We will immediately destroy notes taken during telephone screening conversations with excluded subjects. We will keep records from subjects who are excluded from the study after being enrolled confidential and stored securely as described above.
- Coded blood and urine samples will be sent to LLNL for analysis of study endpoints. Any sample remaining after analysis will be destroyed at LLNL. Coded data will be sent to PNNL for analysis. Coded samples not sent to LLNL will be stored in LPSC 389 at OSU indefinitely unless subjects do not give permission to store samples and data for future studies.
- If a subject does not give permission to use of their data and samples for use in future studies, their samples will be discarded according to OSU Biosafety policies and their data will be excluded from data sets used for future studies.
- This research is covered by a Certificate of Confidentiality from the National Institutes of Health. This Certificate has been deemed issued.

27. Risks

Potential risks of participation in this study are as follows:

BaP: The International Agency for Research on Cancer (IARC) has determined that BaP is a Class 1 known human carcinogen². Humans are exposed to PAHs, including BaP, from a number of sources, the highest being occupational and smoking, so we are excluding these populations. In the general population, the greatest BaP exposure is through diet (9.5-43.5 ng/day inhalation; 1 ng/day water;

160-1,600 ng/day diet)¹⁻⁵. The dietary restrictions during this study are intended to offset the total 425 ng BaP consumed in 4 study cycles. This is equivalent to less than or equal to 4.2 ng/day over the 101 day (minimum) study period. We estimate that following our dietary restrictions will reduce subject daily dietary exposure to BaP by 35-54 ng/day. Therefore, subjects are not exposed to an increased risk of cancer.

Radiation: The total radiation dose of 45.9 nCi for the 4 dose cycles of [¹⁴C]-benzo[a]pyrene is equivalent to about 170 minutes of natural background radiation. The risk from the ultra-low doses in this study is negligible.

Blood Sampling: Risks of blood sampling include pain, bruising, and in rare instances, infection. Some individuals can become lightheaded or nauseated. A qualified research nurse or certified phlebotomist will perform blood draws and carry out all necessary precautions to reduce the risk of injury to subjects.

Blood Loss: While the risk of negative impact due to blood loss is negligible, subjects will be asked to refrain from blood donation one month before the study until one month after completion of the final cycle.

Food allergens: Foods and beverages provided during this study may contain allergens. Ingredient lists and packaged foods with clearly labeled allergen information will be provided to subjects upon request. Subjects will be asked to notify the study nurse of any food allergies before ordering breakfast.

Confidentiality/anonymity: Loss of confidentiality or anonymity is a potential risk. See Confidentiality and Anonymity section.

Reporting of adverse events: Adverse events will be reported to the IRB and the FDA in accordance with each entity's policy.

Data and Safety Monitoring Plan: The *Data and Safety Monitoring Plan* document outlines risks and measures to minimize risk as listed above, reporting frequency and report content that will be provided to NIEHS, FDA and the OSU IRB. We do not have an independent Data and Safety Monitoring Board because this is a single-center study.

28. Benefits

This study is not designed to be of benefit to individual subjects. Potential benefits to society include essential information to aid regulatory agencies with respect to how environmental PAHs, such as BaP, at environmentally relevant levels of exposure are taken up by the G.I. (96% of carcinogenic PAH exposure in humans is dietary), metabolized and excreted from the body. That information can be used in modeling risk assessment rather than high-dose animal studies. This will provide a mechanism for improvement of public health

29. Assessment of Risk:Benefit ratio

The potential benefits in the form of knowledge gained for determination of exposure risk factors and promotion of human health outweigh the potential identifiable minimal risks.

References cited:

1. JEFCA (Joint FAO/WHO Expert Committee on Food Additives), 2005. Exposure to carcinogenic PAHs in the environment. Environm. Sci. Technol. 26, 1278-1284.

2. International Agency for Research on Cancer, 2010. IARC Monographs on the Evaluation of Carcinogenic Risks to Humans. Vol. 92, Some Non-Heterocyclic Polycyclic Aromatic Hydrocarbons and Some Related Exposures, Lyon France.
3. ATSDR, 2013. Priority list of hazardous substances, <https://www.atsdr.cdc.gov/spl/> (accessed 07/11/2017).
4. U.S. EPA (2010) Development of a relative potency factor (RPF) approach for polycyclic aromatic hydrocarbon (PAH) mixtures (External Review Draft), U.S. EPA, Washington, D.C., EPA/635/R-08/012A.

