Subjects will be asked to avoid consuming cruciferous vegetables, I3C or DIM supplements, smoked or cured meat or cheeses, or charcoal-grilled meats for 2 weeks prior to and during each study cycle. Gas-grilled foods are allowed. Subjects will be provided a list of cruciferous vegetables and condiments to avoid.

Subjects will be asked to confirm they have followed the dietary restrictions before study cycle activities begin. Subjects who indicate that they have not followed the diet restrictions for 2 weeks will be allowed to have up to two dietary lapses with subsequent washout extension before they will be automatically removed from study participation due to lack of compliance.

Study cycles (4 total - 25, 50, 100 and 250 ng):

Subjects will be asked to complete a 3-day food diary covering the 3 days prior to each study cycle. Administration of this diary in our current study (IRB protocol 5644) showed that, on average, volunteers decreased their dietary BaP exposure by 35-54 ng/day¹⁶. During the study volunteers are required to keep a similar food diary. The results will be used to estimate dietary intake of PAHs using

the latest data from the Joint FAO/WHO Expert Committee on Food Additives (JECFA, <http://www.food.gov.uk/multimedia/pdfs/poly-aromatic-hydrocarbons.pdf>, accessed 11-7-2016).

Subjects will fast overnight (no food or drink besides water) before Day 1 of each cycle. Subjects will be asked to provide a spot urine sample for baseline analysis and then to empty their bladders completely. Female subjects' urine will also be used for a urine pregnancy test and test results must be negative to proceed with study activities. The results of these pregnancy tests will not be revealed to the subject in compliance with the Oregon Health Authority, Laboratory Compliance Section. Female subjects' pregnancy status will be confirmed via urine test at the start of each of the 4 cycles.

The IV catheter will be placed in an appropriate vein in the forearm or antecubital region by the nurse coordinator. Subjects will swallow a capsule containing the [¹⁴C]-BaP with 100 mL water. Prior to every micro-dosing with [¹⁴C]-BaP, a time zero blood sample of 20 mL will be collected with 10 mL analyzed for background plasma levels of BaP (and 62 additional PAHs) with GC-MS/MS¹⁷ and the remaining 10 mL analyzed for [¹⁴C]-BaP and metabolites as with subsequent time points.

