Blood will be sampled at 0, 0.25 0.5, 1.0, 1.5, 2, 3, 4, 8, 24, and 48 hours (11 draws total, 8-9 of which come from the catheter). The catheter will remain in place for blood draws through hour 4. After the 4 hour blood draw, subjects will have the choice of having the catheter removed and returning for the 8 hour blood draw by straight stick, or they can keep the catheter in place and remain on-site until after the 8 hour blood draw. The subjects will be monitored by the nurse coordinator between blood draws. The 8 (possibly), 24, and 48 hour blood draws will be done with straight stick phlebotomy. No more than three (3) skin punctures will be made in an attempt to draw blood at each visit. The first blood draw of each cycle will be 20 mLs and then subsequent blood draws will be 10 mL for a total amount of 120 mLs (8 tablespoons) per cycle.

Subjects will be instructed to collect all urine during the entire 48-hour study cycle in containers provided by the study team. Subjects will be provided a discrete soft-sided cooler bag to store collected urine samples. They will be instructed to store samples at room temperature between visits and to return any filled containers at their next visit. The longest subjects will need to store samples between visits is 24 hours between Visits 3 and 4.

Two hours after swallowing the capsule, subjects can order breakfast from a menu from Ava's Café or other local cafe, after which subjects may resume normal eating and drinking. Packaged snacks or juice will be provided prior to the standardized breakfast if the study team determines it is necessary.

This process will be followed for each dose (25, 50, 100 and 250 ng [¹⁴C]-BaP) for a total of 4 cycles per subject. There will be at least three weeks' washout period between cycles. Previous multiple micro-dosing of the same individual has shown that after 3 weeks there is no detectable [¹⁴C] in plasma or urine, validating the choice of 3 weeks as adequate for a "washout period"^{7,8}. Extending the washout period will not adversely impact the data collected from the subjects but will minimize the subject's exposure to PAHs.

Subjects will be asked to defer blood donation for one month before, throughout, and for one month after completion of the study. At any point during the study, subjects will be referred to their physician if the study physician or nurse consider this advisable.

Processing of samples:

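### Section 25 gives 240 mL as the most blood drawn in 8 weeks, but the three-week minimum washout in section 18 permits 360 mL

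*Combined protocol and SAP*

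**What the plan says.** Section 18 of the protocol (Methods and Procedures) schedules 11 blood draws from 0 to 48 hours in each cycle. The first is 20 mL and the other ten are 10 mL each, "for a total amount of 120 mLs (8 tablespoons) per cycle". Each subject has four cycles.

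On spacing, section 18 gives a lower limit only: "There will be at least three weeks" of washout between cycles. It adds that "Extending the washout period will not adversely impact the data collected from the subjects". The dietary restriction applies "for 2 weeks prior to and during each study cycle", which fits inside a three-week gap and so does not lengthen it.

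Section 25 (Biological Samples) states: "The total amount of blood collected from each subject is 480 mL", which is four cycles of 120 mL. The next sentence is the one at issue: "The maximum amount of blood collected in an 8 week period is 240 mL".

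Section 27 (Risks) spreads the total BaP dose "over the 101 day (minimum) study period". It does not show how 101 days was reached.

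**The concern.** The section 25 maximum is exactly two cycles' worth of blood. Cycles last 48 hours and may follow each other after three weeks, so three of them appear to fit in 8 weeks.

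This sentence is the only visible statement of how much blood a subject can lose over a limited period, and a reviewer of the protocol would take it as an upper limit. If the scheduling rule does not deliver that limit, staff who follow section 18 can exceed it without noticing. What is at stake is the accuracy of a safety description, not the pharmacokinetic results.

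**Working it through.** **Inputs.** From section 18: 20 mL plus ten draws of 10 mL, draw times from 0 to 48 h, four cycles, and a washout of at least three weeks. From section 25: 480 mL in total and 240 mL in 8 weeks. From section 27: a 101-day minimum. I take 8 weeks as any 56 consecutive days.

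**Figures that reproduce.** Per cycle: 20 + 10 x 10 = 120 mL. Total: 4 x 120 = 480 mL. By day, a cycle takes 100 mL on the dosing day (20 + 8 x 10) and 10 mL on each of the next two days.

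**The 8-week maximum at the permitted minimum spacing.** Three weeks of washout can be counted in three ways.

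| Reading of three weeks | Dose to dose | Doses 1 to 3 on days | Last draw of cycle 3 | Most blood in 56 days |
|---|---|---|---|---|
| Dose to dose | 21 days | 0, 21, 42 | day 44 | 360 mL |
| 48 h draw to next dose | 23 days | 0, 23, 46 | day 48 | 360 mL |
| 21 clear days | 24 days | 0, 24, 48 | day 50 | 360 mL |

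The stated 240 mL does not reproduce under any of them. The excess is 360 - 240 = 120 mL, and 120/240 = 50%. A fourth cycle never fits, because its dose is on day 63 at the earliest.

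**When 240 mL is true.** Let D be the number of days from one dose to the dose two cycles later.

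- D of 53 or less: all three cycles lie in days 0 to 55, giving 360 mL.
- D = 54: the last 10 mL drops out, giving 350 mL.
- D = 55: only the third dosing day is inside, giving 120 + 120 + 100 = 340 mL.
- D of 56 or more: sliding the window forward loses 100, 10 and 10 mL from the earlier cycle no later than it gains the same from the later one, so the window never holds more than 240 mL.

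The worst window is therefore at most 240 mL if and only if dose 3 is at least 56 days after dose 1 and dose 4 is at least 56 days after dose 2. With even gaps, 26 days gives 360 mL, 27 gives 350 mL and 28 gives 240 mL. Uneven schedules can also comply: doses on days 0, 21, 56 and 77 keep a 21-day gap and give 240 mL.

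**Whether the 101-day minimum closes the gap.** Count the study as a 14-day diet lead-in, the first-to-last dose span and 3 days for the last cycle. Four-week spacing then gives 14 + 84 + 3 = 101. Spacing at the section 18 minimum gives 14 + 63 + 3 = 80, 14 + 69 + 3 = 86 or 14 + 72 + 3 = 89. But 101 days limits the total length, not the gaps within it. Doses on days 0, 21, 42 and 84 also count to 101, respect a 21-day dose-to-dose minimum, and put 360 mL in the first 56 days. So do doses on days 0, 24, 48 and 84, which meet all three readings.

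**The case against.** The best reply is that a minimum spacing and a maximum volume are two separate constraints, and a site must meet both. On that reading 240 mL is itself the rule, drawing 360 mL would depart from section 25, and nothing is contradictory. It is true that both sections can be obeyed together. But the sentence sits beside the 480 mL total in a description of samples and is worded as a description. Section 18, from which visits are scheduled, neither repeats it nor points to it. If it is a cap, section 18 should carry it. If it is a description, it is wrong at the permitted minimum.

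The second reply is that 240 mL and 101 days both fit four-week spacing, so the schedule in mind was probably 28 days and the figure is right for it. This is persuasive as to intent and is why the point is minor. It remains an inference. Section 27 gives no derivation and uses 101 only as a divisor (425/101 = 4.2 ng/day). The sum 14 + 4 x 21 + 3 also gives 101, although four cycles have only three gaps between them.

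Third, the Biological Materials Form, the consent pages and the Data and Safety Monitoring Plan are not in the text available, and one of them may hold a scheduling rule. The point is limited to what is visible.

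A reader might go further and infer that subjects will be over-bled or that a safety limit is breached. The documents do not support that. No limit other than the 240 mL statement is exceeded, section 27 calls the risk from blood loss negligible, and blood donation is deferred from one month before to one month after the study. Nor can one say how often 240 mL would be passed, since no actual visit schedule is given.

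**Conclusion.** The concern holds as a minor inconsistency. At the minimum washout that section 18 permits, the most blood drawn in 56 days is 360 mL against a stated 240 mL, under all three readings of three weeks. No visible passage imposes the 56-day condition that would make 240 mL true, and the 101-day minimum does not supply it.

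The conclusion rests on the stated draw volumes and times, on 8 weeks meaning any 56 consecutive days, and on there being no scheduling rule in the material not shown. It does not rest on the inferred breakdown of 101 days.

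Two wider readings should be resisted. The two sections are not irreconcilable, since four-week spacing and some uneven schedules satisfy both. The 101-day figure is not shown to be wrong either, since its derivation is not given. The 480 mL total is correct and the statistical analysis is unaffected.

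**What to change.** Add one clause to section 18: *no more than two cycles in any 8-week period (each dose at least 56 days after the dose two cycles earlier)*. This keeps the three-week washout and makes the section 25 statement true. A simpler but stricter alternative is at least 28 days between consecutive doses. If the sponsor wants neither, restate the section 25 maximum as 360 mL.

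The cost is small. The shortest time from first to last draw changes as follows.

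| Dose-to-dose minimum | At the minimum now | With the two-cycle clause | With 28-day spacing |
|---|---|---|---|
| 21 days | 65 days | 79 (+14) | 86 (+21) |
| 23 days | 71 days | 81 (+10) | 86 (+15) |
| 24 days | 74 days | 82 (+8) | 86 (+12) |

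On the count of 14 + dose span + 3, the two-cycle clause needs 94, 96 or 97 days, inside the stated 101-day minimum, and 28-day spacing needs exactly 101. If that count is what the sponsor meant, neither adds time to the study as planned. Section 18 already says that a longer washout does not harm the data. Restating the figure costs nothing in scheduling.
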